### 5.1 Inclusion Criteria

Subjects are eligible to be included in the study only if all of the following criteria apply:

1. Subjects should be 18 years or older at the time of signing the informed consent during the Screening visit.
2. Subjects with a clinical diagnosis of chronic plaque psoriasis of at least 6 months (as determined by-subject interview and confirmation of diagnosis through physical examination by Investigator).
3. Subjects must have moderate to severe plaque psoriasis of the scalp at Screening and at Baseline, defined by:
  - Scalp Investigator Global Assessment (IGA mod 2011 (scalp) of  $\geq 3$
  - Psoriasis Scalp Severity Index (PSSI) score of  $\geq 12$
  - $\geq 30\%$  or scalp surface area affected.
4. Subject must have moderate to severe plaque psoriasis at Screening and Baseline defined by
  - IGA mod 2011 (whole body) of at least moderate severity (score of  $\geq 3$  on a 5-pointer scale)
  - PASI score of  $\geq 12$
  - Body Surface Area (BSA) involvement of  $\geq 10\%$
5. Subjects must be considered candidates for systemic therapy, meaning scalp psoriasis inadequately controlled by topical treatments (corticosteroids), and/or phototherapy, and/or previous systemic therapy.
6. Subjects has a negative evaluation for tuberculosis (TB) within 4 weeks before initiating study treatment, defined as a negative QuantiFERON® test. Subjects with a positive or 2 successive indeterminate. QuantiFERON® tests are allowed if they have all of the following:
  - No history of active TB or symptoms of TB.
  - A posterior-anterior chest radiogram (with associated report available at study center) performed within 3 months of Screening with no evidence of active TB (or of any other pulmonary infectious diseases).
  - If prior latent TB infection (LTBI), must have history of adequate prophylaxis (per local standard of care).
  - If presence of LTBI is established, then treatment according to local country guidelines must have been followed for 4 weeks prior to inclusion in the study.

A maximum of 2 QuantiFERON® tests are allowed. A re-test is only permitted if the first is indeterminate; the result of the second test will then be used.

7. Subjects are unlikely to conceive, as indicated by at least one “Yes” answer to the following questions:
  - Subject is a male.
  - Subject is a female and agrees to abstain from heterosexual activity OR use a highly effective method of contraception as per [Appendix 7](#).

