**8.2.1 Physical Examinations**

- A complete physical examination will include assessments of general appearance; skin; head/neck [REDACTED]
- A detailed examination of the skin should be performed [REDACTED] for the efficacy assessments [REDACTED]
- Height and weight will also be measured and recorded at Baseline before administration of study treatment.
- Investigators should pay special attention to clinical signs related to previous serious illnesses.

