#### **9.4.2.2 Physical Examinations, 12-Lead ECG, Vital Signs and Clinical Safety Laboratory Tests (Hematology, Biochemistry, and Urinalysis)**

Summaries and listings of data for physical examination findings, vital signs, hematology, biochemistry, and urinalysis laboratory tests will be presented. Appropriate descriptive statistics will be summarized for the observed value at each scheduled assessment and for the corresponding change from Baseline.

For hematology and biochemistry tests, listings of subject data will also flag up any abnormal or out-of-range values. Clinically significant changes in the laboratory test parameters will be summarized and listed. Hematology and clinical laboratory data will be reported in System International units.

Descriptive statistics will be used to present the safety outcomes including, physical examination results, weight, body mass index, 12-Lead ECG, vital signs measurements, and clinical laboratory test results.

Change from Baseline will also be summarized for vital signs measurements and clinical laboratory test results.

All ECG data results (normal/abnormal) will be summarized using frequency and percentages. Clinically significant abnormalities will be presented in by-subject listings.

The incidence of treatment-emergent abnormal laboratory, vital sign, and ECG values will also be summarized using descriptive statistics.

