903 COVID-19 related adverse events may also be summarized separately if deemed necessary.

904 **4.10.2 Clinical Laboratory Evaluation**

905 Absolute values and changes from Baseline of clinical laboratory data (hematology,
906 chemistry, continuous urinalysis parameter and lipids) will be summarized with descriptive
907 statistics at Baseline, and Week 16 [REDACTED] at the interim [REDACTED]
[REDACTED]

912 All clinical laboratory data relevant to the reporting period [REDACTED] will be
913 listed by subject. Values outside the normal ranges will be flagged. Flags will describe
914 direction relative to normal range in relevant parameters.

915 **4.10.3 Vital Signs**

916 Vital signs measurements including temperature, pulse rate, systolic blood pressure, and
917 diastolic blood pressure, respiratory rate at each scheduled visit and changes from baseline
918 during the treatment period will be summarized by treatment arm. Vital signs will also be
919 presented in a shift table displaying the cross tabulation of the Baseline result category versus
920 the result of the post-treatment period at each scheduled visit. The categories of each vital
921 sign parameters are as below:

923 **4.10.4 12-Lead Electrocardiogram (ECG)**

924 The ECG measurements at each scheduled visit [REDACTED]
[REDACTED] and change from baseline
926 during the treatment period will be summarized by treatment arm.

927 All ECG measurements and the overall interpretation will be listed by subject [REDACTED]
[REDACTED]

930 **4.10.5 Physical Examinations**

931 The frequency of subjects with abnormal evaluations of body system findings for physical
932 examinations will be summarized by visit and treatment group; abnormal physical
933 examination findings will also be presented in a by-subject listing.

934 **4.10.6 Performance Status**

935 Not applicable.

936 **4.10.7 Other Safety Parameters**

937 The subjects will be assessed for suicidal ideation and behavior using Columbia-Suicide
938 Severity Rating Scale (C-SSRS) at screening, baseline and each subsequent visit. C-SSRS
939 contains two categories: (1) Suicidal Ideation (questions 1-5), most severe ideation will also be
940 collected; (2) Suicidal behavior (questions 6-10).

941 The following outcomes are C-SSRS categories and have binary responses (yes/no). The
942 categories listed below have been re-ordered from the actual scale in an increasing order of

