943 severity from 1 to 10 to facilitate the definitions of the comparative endpoints.

944 **Table 2** C-SSRS Outcomes

Categories
Suicidal Ideation (1-5)
1 – Wish to be dead
2 – Non-specific active suicidal thoughts
3 – Active suicidal ideation with any methods (not plan) without intent to act
4 – Active suicidal ideation with some intent to act, without specific plan
5 – Active suicidal ideation with specific plan and intent

Categories
Suicidal behavior (6-10)
6 – Preparatory acts or behavior
7 – Aborted attempt
8 – Interrupted attempt
Suicidal acts (9-10)
9 – Non-fatal suicide attempt
10 – Completed suicide

945 The following are numerical scores derived from the above C-SSRS categories.

- 946 • Suicidal Ideation Score: The maximum suicidal ideation category (1-5 on the C-SSRS)
947 present at the assessment. Assign a score of 0 if no ideation is present.
- 948 • Suicidal Behavior Score: The maximum suicidal behavior category (6-10 on the
949 C-SSRS) present at the assessment. Assign a score of 0 if no behavior is present.
- 950 • Suicidal Ideation or Behavior Score: The maximum suicidal ideation or behavior
951 category (1-10 on the C-SSRS) present at the assessment. Assign a score of 0 if no
952 ideation or behavior is present.

953 Subjects are also classified into two risk levels:

- 954 • Intermediate risk level is indicated by a response of “yes” to Questions 1 to 3 and the
955 absence of a “yes” response to Questions 4 and 5.
- 956 • High risk level is indicated by a response of “yes” to Questions 4 or 5 in the suicidal
957 ideation section, or any positive response in the behavioral section of the C-SSRS.

958 Change in binary response to the questions from no to yes in any questions will be summarized
959 in a shift table describing baseline vs post-baseline per visit, and worst post-baseline overall.
960 Categorical scores will be analyzed similarly. C-SSRS risk levels are also summarized by visit.
961 Results from the C-SSRS will be listed by subject. Results to Week 16 will be described in the
962 Part 1 interim analysis, and overall results to Week 52 and 72 will be described in the final
963 analysis.

964 4.11 Sensitivity and Subgroup Analyses

965 Sensitivity and subgroup analyses will be performed to confirm the robustness of primary
966 analysis results.

[REDACTED]
[REDACTED]

[REDACTED]
[REDACTED]
[REDACTED]

[REDACTED]
[REDACTED]
[REDACTED]

[REDACTED]

[REDACTED]

[REDACTED]
[REDACTED]
[REDACTED]

[REDACTED]
[REDACTED]

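### The physical-examination safety table counts abnormal findings visit by visit with no within-subject reference to Baseline, so its skin row cannot be read as a safety comparison if psoriasis is recorded as abnormal

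*SAP*

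**What the plan says.** SAP 4.10.5 summarizes "The frequency of subjects with abnormal evaluations of body system findings for physical" examinations; the sentence continues that "examinations will be summarized by visit and treatment group; abnormal physical" "examination findings will also be presented in a by-subject listing". The section contains nothing else. Its printed line numbers run without a break, so no part of it is blacked out.

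Other safety data are treated differently. SAP 4.10.2 (laboratory) and 4.10.4 (ECG) plan change from Baseline. SAP 4.10.3 plans change from Baseline for vital signs and also has them "presented in a shift table displaying the cross tabulation of the Baseline result category versus" later results. SAP 4.10.7 puts C-SSRS changes "in a shift table describing baseline vs post-baseline per visit, and worst post-baseline overall".

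Protocol 8.2.1 describes the examination: "A complete physical examination will include assessments of general appearance; skin; head/neck", with the rest of the list redacted. Protocol 5.1, criterion 3, requires scalp disease at Screening and Baseline, with at least 30% of the scalp surface affected. Criterion 4 adds body disease: "Subject must have moderate to severe plaque psoriasis at Screening and Baseline defined by" a PASI of at least 12 and at least 10% body surface area, among other measures.

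Protocol 9.4.2.2 names physical-examination findings together with vital signs and laboratory tests, and then says: "Appropriate descriptive statistics will be summarized for the observed value at each scheduled assessment and for the corresponding change from Baseline".

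**The concern.** A count of abnormal findings at each visit measures prevalence. It becomes a safety measure only when a reader can tell what is new. For most body systems, omitting Baseline merely adds pre-existing findings to both arms.

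Skin is different in this trial, because entry requires skin disease and the active drug is expected to clear it. If psoriasis is recorded as an abnormal skin finding, the row starts close to 100% in both arms and then drops faster on tildrakizumab. A reader of the safety tables would see a difference in favour of the drug that comes from efficacy. Meanwhile a subject who still has plaques and develops an unrelated skin finding is already counted as abnormal, so the count does not move.

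**Working it through.** The documents give no figure for this point, so there is none to reproduce. The check compares the sections and then illustrates the mechanism under assumptions.

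**Baseline reference by type of safety data (SAP)**

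| Data | Section | Baseline reference |
|---|---|---|
| Laboratory | 4.10.2 | change |
| Vital signs | 4.10.3 | change and shift table |
| ECG | 4.10.4 | change |
| C-SSRS | 4.10.7 | shift table, per visit and worst |
| Physical examination | 4.10.5 | none |

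**Illustration for the skin row at Week 16.** From the documents: n = 107 per arm (Protocol 4.1). Assumed, not from the documents:
- c, the share of subjects with no residual psoriasis on examination: 10%, 30% or 50% on active, paired with 0%, 2% or 5% on placebo.
- q, the share with a new non-psoriasis skin finding: 5% in both arms, so there is no true safety difference.
- Psoriasis is recorded as abnormal, and new findings are independent of clearance.

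A subject is normal in the row only if clear and without a new finding. Hence:
- Row count = n × (1 − c × (1 − q))
- Active-minus-placebo difference = −(c active − c placebo) × (1 − q)
- New findings present = n × q = 107 × 0.05 = 5.35 per arm
- New findings that change the row count = n × c × q
- Share of new findings that leave the count unchanged = 1 − c

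| c active / placebo | Row count active / placebo | Difference (points) | New findings that change the count, active / placebo | Unchanged, active / placebo |
|---|---|---|---|---|
| 10% / 0% | 96.8 / 107.0 | −9.5 | 0.5 / 0.0 | 90% / 100% |
| 30% / 2% | 76.5 / 105.0 | −26.6 | 1.6 / 0.1 | 70% / 98% |
| 50% / 5% | 56.2 / 101.9 | −42.75 | 2.7 / 0.3 | 50% / 95% |

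Middle row, worked: 107 × (1 − 0.30 × 0.95) = 76.5; 107 × (1 − 0.02 × 0.95) = 105.0; −(0.30 − 0.02) × 0.95 = −26.6 points.

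Varying q from 1% to 10% moves the extremes of the difference to −44.6 (−0.45 × 0.99) and −9.0 (−0.10 × 0.90). The share left unchanged does not depend on q.

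**Would a plain shift table repair it?** Not for skin. On the same premise nearly everyone is abnormal at Baseline, so a normal-to-abnormal cell is almost empty whatever happens later. Only a flag for new or worsened findings, with psoriasis set apart, recovers the 5.35 per arm.

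**The case against.** The other side has four substantial arguments.

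- **Other routes capture what matters most.** A reader might infer that a skin cancer or drug eruption would go unseen. The documents do not support that. Protocol Appendix 4 makes a clinically significant abnormal safety assessment an adverse event, including one that worsens from Baseline. SAP 4.10.1 summarizes melanoma, non-melanoma skin cancer and treatment-related hypersensitivity as events of special interest, by treatment received. SAP 4.10.5 itself lists abnormal findings by subject. This argument stands and limits the point to the tabulated view.
- **The protocol may not ask for more.** A reader might infer that SAP 4.10.5 departs from Protocol 9.4.2.2. One sentence there can be read that way. However, a later sentence on change from Baseline names only vital signs and laboratory results, and the treatment-emergent summary names only laboratory, vital-sign and ECG values. The wording is ambiguous, so a clear departure is not shown.
- **The premise is unverified.** No visible text says whether investigators record the study disease as an abnormal examination finding, or code scalp lesions under head/neck. Protocol 8.2.1 is partly redacted, and psoriasis extent is captured separately by the efficacy scales. This stands as a condition on the conclusion: a plausible one for skin, weaker for head/neck.
- **The display may show more than the text says.** The visits tabulated may include Baseline, which would reveal high entry prevalence. That allows a comparison of groups, not of a subject with his or her own Baseline. A shift layout in redacted SAP pages cannot be excluded, but 4.10.5 does not call for one.

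**Conclusion.** The point holds as a minor, inexpensive improvement to a descriptive safety table. The primary efficacy analysis is unaffected.

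The text establishes that physical examination is the one type of safety data among these five with no planned Baseline reference, and that every subject enters with body and scalp psoriasis. If psoriasis is recorded as an abnormal finding, the skin row cannot separate new findings from the study disease or its clearance. It is then not interpretable between arms. Head/neck follows only if scalp lesions are coded there. Other body systems lack just the usual Baseline reference.

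It would go too far to say that no new skin finding can ever register. A subject who has cleared can become abnormal again and be counted, and the illustration allows for this.

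The actual size is not derivable from the documents. The illustrated differences of roughly −9 to −45 points rest entirely on assumed clearance and finding rates. What is lost is a between-arm table of new findings, mainly those not judged clinically significant.

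**What to change.** In SAP 4.10.5, tabulate the number of subjects with a physical-examination finding that is new or worsened since Baseline, by body system, Part and treatment received. Identify psoriasis lesions separately from other skin and head/neck findings. Keep the by-subject listing. Do not rely on a normal-to-abnormal shift alone.

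Reconcile the section with Protocol 9.4.2.2 by stating which of its change-from-Baseline sentences apply to physical examination.

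The cost is SAP wording, one table and a blinded review of finding text to flag new or worsened findings and to separate psoriasis from other findings. The review can be only as good as the detail recorded for each finding, and the visible documents do not show how much is collected.

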SUICIDAL BEHAVIOR (Check all that apply, so long as these are separate events; must ask about all types)			Past X Years or Lifetime		
Actual Attempt: A potentially self-injurious act committed with at least some wish to die, as a result of act . Behavior was in part thought of as method to kill oneself. Intent does not have to be 100%. If there is any intent/desire to die associated with the act, then it can be considered an actual suicide attempt. There does not have to be any injury or harm , just the potential for injury or harm. If person pulls trigger while gun is in mouth but gun is broken so no injury results, this is considered an attempt. Inferring Intent: Even if an individual denies intent/wish to die, it may be inferred clinically from the behavior or circumstances. For example, a highly lethal act that is clearly not an accident so no other intent but suicide can be inferred (e.g., gunshot to head, jumping from window of a high floor/story). Also, if someone denies intent to die, but they thought that what they did could be lethal, intent may be inferred. Have you made a suicide attempt? Have you done anything to harm yourself? Have you done anything dangerous where you could have died? What did you do? Did you _____ as a way to end your life? Did you want to die (even a little) when you _____? Were you trying to end your life when you _____? Or did you think it was possible you could have died from _____? Or did you do it purely for other reasons / without ANY intention of killing yourself (like to relieve stress, feel better, get sympathy, or get something else to happen)? (Self-Injurious Behavior without suicidal intent) If yes, describe:			Yes 	No 	Total # of Attempts _____

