## 2) C-SSRS Baseline

# COLUMBIA-SUICIDE SEVERITY RATING SCALE (C-SSRS)

Baseline

Version 1/14/09

*Posner, K.; Brent, D.; Lucas, C.; Gould, M.; Stanley, B.; Brown, G.; Fisher, P.; Zelazny, J.;  
Burke, A.; Oquendo, M.; Mann, J.*

*Disclaimer:*

*This scale is intended to be used by individuals who have received training in its administration. The questions contained in the Columbia-Suicide Severity Rating Scale are suggested probes. Ultimately, the determination of the presence of suicidal ideation or behavior depends on the judgment of the individual administering the scale.*

*Definitions of behavioral suicidal events in this scale are based on those used in The Columbia Suicide History Form developed by [name] and [name], Conte Center for the Neuroscience of Mental Disorders (CCNMD), New York State Psychiatric Institute, [name]. (Oquendo M. A., Halberstam B. & Mann J. J., Risk factors for suicidal behavior: utility and limitations of research instruments. In M.B. First [Ed.] Standardized Evaluation in Clinical Practice, pp. 103 -130, 2003.)*

*For reprints of the C-SSRS contact [name]., New York State Psychiatric Institute, [name]; inquiries and training requirements contact [[contact]](mailto:[contact])*

© 2008 The Research Foundation for Mental Hygiene, Inc.

SUICIDAL IDEATION		Lifetime: Time He/She Felt Most Suicidal		

Ask questions 1 and 2. If both are negative, proceed to "Suicidal Behavior" section. If the answer to question 2 is "yes", ask questions 3, 4 and 5. If the answer to question 1 and/or 2 is "yes", complete "Intensity of Ideation" section below.
				

1. Wish to be Dead Subject endorses thoughts about a wish to be dead or not alive anymore, or wish to fall asleep and not wake up. Have you wished you were dead or wished you could go to sleep and not wake up?
 
If yes, describe:
		
Yes No
 
 
		

2. Non-Specific Active Suicidal Thoughts General, non-specific thoughts of wanting to end one's life/commit suicide (e.g., "I've thought about killing myself") without thoughts of ways to kill oneself/associated methods, intent, or plan. Have you actually had any thoughts of killing yourself?
 
If yes, describe:
		
Yes No
 
 
		

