## 3) C-SSRS Since Last Visit

# COLUMBIA-SUICIDE SEVERITY RATING SCALE (C-SSRS)

Since Last Visit

Version 1/14/09

*Posner, K.; Brent, D.; Lucas, C.; Gould, M.; Stanley, B.; Brown, G.; Fisher, P.; Zelazny, J.;  
Burke, A.; Oquendo, M.; Mann, J.*

*Disclaimer:*

*This scale is intended to be used by individuals who have received training in its administration. The questions contained in the Columbia-Suicide Severity Rating Scale are suggested probes. Ultimately, the determination of the presence of suicidal ideation or behavior depends on the judgment of the individual administering the scale.*

*Definitions of behavioral suicidal events in this scale are based on those used in The Columbia Suicide History Form developed by [name] and [name], Conte Center for the Neuroscience of Mental Disorders (CCNMD), New York State Psychiatric Institute, [name]. (Oquendo M. A., Halberstam B. & Mann J. J., Risk factors for suicidal behavior: utility and limitations of research instruments. In M.B. First [Ed.] Standardized Evaluation in Clinical Practice, pp. 103 -130, 2003.)*

*For reprints of the C-SSRS contact [name]., New York State Psychiatric Institute, [name]; inquiries and training requirements contact [[contact]](mailto:[contact])*

© 2008 The Research Foundation for Mental Hygiene, Inc.

SUICIDAL IDEATION						

Ask questions 1 and 2. If both are negative, proceed to "Suicidal Behavior" section. If the answer to question 2 is "yes", ask questions 3, 4 and 5. If the answer to question 1 and/or 2 is "yes", complete "Intensity of Ideation" section below.
		Since Last Visit				

1. Wish to be Dead                      Subject endorses thoughts about a wish to be dead or not alive anymore, or wish to fall asleep and not wake up.  Have you wished you were dead or wished you could go to sleep and not wake up?
 
If yes, describe:
	Yes    No  					

2. Non-Specific Active Suicidal Thoughts                      General non-specific thoughts of wanting to end one's life/commit suicide (e.g., "I've thought about killing myself") without thoughts of ways to kill oneself/associated methods, intent, or plan during the assessment period.  Have you actually had any thoughts of killing yourself?
 
If yes, describe:
	Yes    No  					

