311 Unless otherwise specified, “Baseline” is defined as the last observed value of the parameter
312 of interest prior to the first intake of study treatment (this includes unscheduled visits). For
313 numerical variables, change from Baseline will be calculated as the difference between the
314 post-Baseline value and the corresponding Baseline value. Change from Baseline is defined
315 as: post-Baseline value – Baseline value. The percent change from Baseline will be calculated
316 as change from Baseline divided by the Baseline value, expressed as a percentage.

317 4.2 Determination of Sample Size

318 The study will randomize approximately 107 subjects per treatment arm (Total N=214) [REDACTED]
319 randomization to either tildrakizumab 100 mg arm (Arm A) or placebo arm (Arm B),

[REDACTED]

[REDACTED]

340

[REDACTED]

[REDACTED]

360 **4.3 Disposition of Subjects**

361 The number and frequency of subjects who were screened, screen failures (overall and by
362 reason of screen failure), randomized, completed (overall and by each part of the study), and
363 discontinued (overall and by each part of the study) will be presented. A summary of reasons
364 for discontinuation will be provided. [REDACTED]

[REDACTED]

369 Due to the outbreak of COVID-19 pandemic, COVID-19 related subject
370 disposition events will be further summarized per FDA Guidance on Conduct of Clinical
371 Trials of Medical Products during COVID-19 Public Health Emergency (thereinafter referred
372 to as FDA COVID-19 Guidance)^a, for the following:

- 372 • Number of subjects discontinued from the study for reasons related to COVID-19
- 373 • Number of subjects with visits altered (e.g., remote visits) or missed due to
374 COVID-19
- 375 • Number of subjects with any efficacy assessments not done at each visit due to
376 COVID-19 associated criteria.

[REDACTED]

378 **4.4 Data Sets Analyzed**

379 The following analysis sets will be used in the study:

380 **Intent-to-Treat (ITT) Set:** All randomized subjects who have been dispensed study
381 [REDACTED]

382 **Modified Intent-to-Treat (mITT) Set:** [REDACTED]
[REDACTED]

[REDACTED]
[REDACTED]
[REDACTED]

387 **Uniform Intent-to-Treat (uITT) Set:** [REDACTED]
[REDACTED]

[REDACTED]

389 **Safety Analysis Set (SAF):** All randomized subjects who have received [redacted] dose of
390 study treatment.

391 **Per Protocol Set (PP):** All subjects [redacted] who have completed the [redacted]

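### SAP 4.10.7 compares lifetime-recall C-SSRS baseline answers with since-last-visit answers, so on-study ideation on a question already positive for lifetime is not counted as a no-to-yes change

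*SAP*

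**What the plan says.** SAP 4.10.7 (Other Safety Parameters) schedules the C-SSRS at Screening, at baseline and at every later visit. Its change analysis is "Change in binary response to the questions from no to yes in any questions will be summarized" "in a shift table describing baseline vs post-baseline per visit, and worst post-baseline overall". The derived scores, each being the highest category found at an assessment, are handled in the same way. Risk levels are summarized by visit and all results are listed.

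The section does not say which form or recall period supplies the baseline, so the general rules apply. SAP 4.1.1 says "Unless otherwise specified, “Baseline” is defined as the last observed value of the parameter" before first dosing. SAP 6.2.1 takes the baseline-visit evaluation and uses an earlier one only if that is missing.

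Protocol Appendix 19 prints three forms:

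- **Screening:** ideation over a past number of months, with the number left as X; behavior over "Past X Years or Lifetime".
- **Baseline:** a single ideation column, "Lifetime: Time He/She Felt Most Suicidal", and a lifetime behavior column.
- **Follow-up:** "Since Last Visit" for both ideation and behavior.

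Exclusion 15 (Protocol 5.2) covers subjects judged at high risk at Screening. Its C-SSRS indicators are Question 4 or 5 positive within 12 months, or any positive behavioral item.

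**The concern.** A shift table shows change only if both sides measure the same thing over comparable periods. Here one side is the worst state ever recalled and the other is the interval between two visits. A subject who had passive ideation years ago, was well before dosing, and reports the same ideation on treatment falls in the yes-to-yes cell. If the old episode was more severe, the score appears to improve. Every quiet visit in a subject with any lifetime ideation also appears as an improvement that treatment did not cause.

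This is the only change-from-baseline summary that the SAP states for suicidality. It matters most after Week 16, when the placebo arm has switched to tildrakizumab and there is no concurrent control. From then on, comparison with the pre-treatment state carries most of the interpretation.

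**Working it through.** The plan gives no figure on this point, so there is none to reproduce. The check is of logic and of answer patterns.

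**1. Which form is the reference.** SAP 4.1.1 and 6.2.1 both select the baseline-visit assessment. In Appendix 19 that is the lifetime form. Nothing in the readable text of 4.10.7 overrides this.

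**2. Who can carry a lifetime yes into the trial.** Exclusion 15 limits Questions 4 and 5 to the last 12 months and does not name Questions 1 to 3. Subjects with any history on Questions 1 to 3, or with Question 4 or 5 ideation more than 12 months old, can be enrolled. Positive behavioral items are an exclusion indicator with no 12-month limit, so few subjects should have a behavioral yes at baseline.

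**3. What the no-to-yes rule catches.** The form asks Questions 3 to 5 only if Question 2 is yes.

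- Patterns with Question 2 = no: 2 (Question 1 yes or no).
- Patterns with Question 2 = yes: 2 × 2³ = 16.
- Total 2 + 16 = 18, of which 17 contain at least one yes.

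For each lifetime baseline, the on-study patterns with at least one question that is no at baseline and yes afterwards are:

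| Lifetime baseline | Counted as no-to-yes |
|---|---|
| No ideation | 17 of 17 |
| Question 1 only | 16 of 17 |
| Questions 1–2 | 14 of 17 |
| Questions 1–3 | 12 of 17 |
| All five | 0 of 17 |

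For example, with Questions 1–3 positive for lifetime, the uncounted patterns are 1; 2; 1+2; 2+3; and 1+2+3. That is five, and 17 − 5 = 12.

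Over all 17 × 17 = 289 pairs with some lifetime and some on-study ideation, 199 are counted and 289 − 199 = 90 are not.

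**4. Scores and nested answers.** The ideation score rises only if the on-study maximum exceeds the lifetime maximum. This happens in 100 of the 289 pairs, so the score shift is less sensitive than the question-level shift. If answers are treated as nested by highest level (1 to 5), the on-study level exceeds the lifetime level in 4 + 3 + 2 + 1 + 0 = 10 of 25 combinations. The other 15 show no no-to-yes change.

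**5. With a recent reference.** If the recent-recall reference is negative for ideation, all 17 on-study patterns count, whatever the lifetime history.

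These are counts of patterns, not probabilities. Subjects will not be spread evenly over them.

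**The case against.** Several points on the other side stand.

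- **The rule works per question.** A subject with only a past wish to be dead who newly reports active ideation is counted. A reader might infer that new ideation never counts in anyone with past ideation. The documents do not support that: it holds only for questions already positive, and for all ideation only when all five are.
- **Events are not hidden.** Risk levels by visit use each visit's own answers, yes-to-yes cells would appear in a full shift table, and every result is listed. In Part 1 the randomized arms can be compared by visit without a baseline. What remains is misclassified change: the by-visit summaries do not separate new from continuing ideation, and the baseline risk level has the same lifetime recall.
- **The reference could be set elsewhere.** Protocol 8.2.3 is partly redacted, SAP 4.1.1 allows exceptions, and SAP 6.2 refers to table mock-ups that are not in the documents. The readable part of 4.10.7, which governs this analysis, sets no exception.
- **The Screening form is not a perfect substitute.** X is blank, any window of months is longer than most visit intervals, and Screening may precede Day 1 by up to 28 days. These points shape the fix but do not justify the lifetime reference.
- **The role is limited.** C-SSRS is neither a listed primary safety endpoint nor an adverse event of special interest, and safety analyses are descriptive.

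**Conclusion.** The point holds in limited form and should be corrected. Followed as written, the SAP sets lifetime recall against since-last-visit recall. Ideation on a question already positive for lifetime is then not counted as a no-to-yes change, scores show worsening only above the lifetime worst, and visits without ideation look like improvement. New higher-level ideation is still counted, and behavior is little affected. The efficacy analyses are not touched.

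The number of subjects affected cannot be computed, because the documents give no rate of past or on-study ideation. A reader might still infer that a large share of on-study ideation is missed, but any such figure follows from assumed rates. Suppose 10% of 214 subjects have lifetime ideation, 5% of them have a recurrence, and every recurrence is masked: 214 × 0.10 × 0.05 = 1.07 subjects.

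- With 1% new ideation in the rest (214 × 0.90 × 0.01 = 1.93), the masked share is 1.07 / 3.00 = 36%.
- With 5% in the rest (9.63), it is 1.07 / 10.70 = 10%.

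Full masking also contradicts the per-question rule, so neither share is an estimate.

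The conclusion assumes that the forms in Appendix 19 were used at the visits they are named for, and that no redacted text or mock-up sets another reference.

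**What to change.** Amend SAP 4.10.7 as follows:

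1. Set a C-SSRS-specific reference for the ideation shift tables and scores: the recent-recall ideation column of the Screening form. State the recall period X that was used.
2. Say how ideation first reported between Screening and first dose is handled, so that it is not labelled treatment-emergent by default.
3. State the reference period for behavior, since the Screening form leaves it as years or lifetime.
4. Define treatment-emergent ideation or behavior as absent from, or more severe than, that reference.
5. Show lifetime history as a separate column.
6. Reconcile the text with any reference period given in the redacted part of Protocol 8.2.3.

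The cost is SAP wording, a small change of derivation and an explicit exception to the general baseline rule. Both forms are already scheduled, so no new data are needed provided X was fixed when the Screening form was used. One limitation remains: the recent window is still longer than the interval between visits, so the mismatch shrinks but does not disappear.
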